#### Material and methods:

IHC testing of PD-L1 expression level in tumor tissue samples will be conducted using VENTANA PD-L1 (SP263) Rabbit Monoclonal Primary Antibody. PD-L1 expression for both TC and IC in the tumor microenvironment will be determined by the percentage of cells expressing PD-L1 at any intensity above background staining. PD-L1 will be defined as high if either  $\geq 25\%$  of TC or  $\geq 25\%$  of IC expressed PD-L1, and PD-L1 was defined as low if both,  $<25\%$  of TC and,  $<25\%$  of IC expressed PD-L1.

#### Mutations analysis:

The germline mutations in follow panel of genes will be analysed by NGS:

TP53 MLH1 MSH2 MSH6 PMS2 EPCAM APC MUTYH CDKN2A CDK4 ATM KIT PDGFRA CDH1 CTNNA1 PRSS1 SPINK1 BRCA1 BRCA2 FANCI FANCL PALB2 RAD51B RAD51C RAD54L RAD51D CHEK1 CHEK2 CDK12 BRIP1 PPP2R2A BARD1 PARP1 STK11 XRCC3

DNA from tissue samples will be extracted using a QIAamp DNA Blood Mini Kit. DNA concentration will be measured on the spectrophotometer NanoVue Plus ( «GE Healthcare»). Preparing sequencing library will be performed using NimblGen SepCapEZ Choice («Roche»).

Sequencing will be performed on the Illumina MiSeq ( «Illumina»).

Bioinformatic analysis will be conducted as follows:

1. Trimming the adapter sequences and low-quality reads and using Cutadapt and Trimmomatic.
2. Mapping reads to a reference genome sequence (GRch37/hg19) using the algorithm BWA-MEM.
3. Quality control of input data, alignment, concentration and coverage of target regions using FastQC, BAMQC and NGSrich. Expected covering target regions - by up to 400x-600x, the proportion of target regions covered above 100x - at least 95%, which will detect somatic mutation content of about 1%.
4. Search for the nucleotide variation germinal mutations using GATK HaplotypeCaller + UnifiedGenotyper (to produce a combined VCF-file).
5. Search for the nucleotide variation of somatic mutations via Mutect2 + Strelka (to produce a combined VCF-file).
6. Processing consensus VCF-files using the program SnpSift (filter - read depth more than 10).
7. Annotation using SnpEff (analysis of all transcripts), ANNOVAR (allele frequency analysis ExAC, 1000G and ESP6500, algorithms the functional significance SIFT, PolyPhen2, Mutation Taster, FATMM, CADD, DANN, Eigen) and Alamut Batch (effect on splicing, database dbSNP, ClinVar, HGMD Professional), BIC database.

[figure not shown]
This pipeline has the following characteristics in the analysis our target panel of genes (exons + 50 bp flanking intron regions) with sample NA12878-GIABv3.2 (Precision FDA platform):

Precision: 100%

Recall: 100%

F-Measure:100%

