### **2.2 Secondary objectives**

- To study the frequency of germline mutations forming the familial breast cancer in Tatarstan and Bashkortostan republics.
- To estimate the relation of the frequency of PD-L1 expression in tumor or/and immune cells with disease stage, receptor status (ER, PR, HER2neu), morphological type, Grade
- To estimate the relation of number of tumor-infiltrating lymphocytes (TILs) with disease stage, receptor status (ER, PR, HER2neu), morphological type, Grade and presence of clinically significant mutations in genes of DNA-repair system.

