### Study Flow Chart

**Table 1** **Study Plan**

Study procedures	Screening/ Baseline Visit (day 0)	Biomarker analysis	
		Detection of presence/absence of germline mutations in DNA- repair system genes (NGS)  (1-3 months after day 0)	Estimation of PD-L1 expression level and TILs (IHC)  (1 month after NGS results)
Informed consent	X		
Patient demographics	X		
Medical history	X		
Inclusion / Exclusion criteria	X		
Receiving of blood samples for NGS	X		
Genetic testing		X	
Request of FFPE tumor tissue samples for IHC	X		
IHC			X
Disease information	X		

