### **13.3 Description of analysis sets**

All Enrolled set will consist of all the subjects who signed informed consent to enter the study. Patient disposition and baseline characteristics and demography as well as analysis of the primary and secondary objectives will be based on the set.

All patients will be enrolled in 2 groups 1:1. The analyses of primary objective will be conducted based on the results in these groups:

- The investigated group will be consists of patients with clinical features of hereditary BC (according to NCCN breast and/or ovarian cancer genetic assessment guidelines V1.2017) and revealed clinically significant (pathogenic) germline mutations in DNA-repair genes (TP53 MLH1 MSH2 MSH6 PMS2 EPCAM APC MUTYH CDKN2A CDK4 ATM KIT PDGFRA CDH1 CTNNA1 PRSS1 SPINK1 BRCA1 BRCA2 FANCI FANCL PALB2 RAD51B RAD51C RAD54L RAD51D CHEK1 CHEK2 CDK12 BRIP1 PPP2R2A BARD1 PARP1 STK11 XRCC3) regardless morphological type, grade, receptor status and extent of the disease.

- The control group will be consisting of patients with sporadic BC without germline mutations in DNA-repair genes (TP53 MLH1 MSH2 MSH6 PMS2 EPCAM APC MUTYH CDKN2A CDK4 ATM KIT PDGFRA CDH1 CTNNA1 PRSS1 SPINK1 BRCA1 BRCA2 FANCI FANCL PALB2 RAD51B RAD51C RAD54L RAD51D CHEK1 CHEK2 CDK12 BRIP1 PPP2R2A BARD1 PARP1 STK11 XRCC3) regardless morphological type, grade, receptor status and extent of the disease.

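### The written NGS pipeline has no step for exon-level deletions or duplications, so the familial mutation frequency can only be biased downward by this class; the primary comparison is little affected

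*Combined protocol and SAP*

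**What the plan says.** Section 3.1 (Mutations analysis) lists seven bioinformatic steps. Two of them call variants:

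- Germline: "Search for the nucleotide variation germinal mutations using GATK HaplotypeCaller + UnifiedGenotyper (to produce a combined VCF-file").
- Somatic: "Search for the nucleotide variation of somatic mutations via Mutect2 + Strelka (to produce a combined VCF-file").

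The steps before these trim, map and check quality. The steps after them work on the files already produced: "Processing consensus VCF-files using the program SnpSift (filter - read depth more than 10"), and then annotation. Performance is introduced with "This pipeline has the following characteristics in the analysis our target panel of genes (exons + 50 bp flanking intron regions) with sample NA12878-GIABv3.2", followed by precision, recall and F-measure of 100% each.

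Carrier status comes from this source alone. The only determination in Table 1 (Study Plan) is "Detection of presence/absence of germline mutations in DNA- repair system genes (NGS"). The result is used in three places:

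- Section 2.2, first secondary objective: "To study the frequency of germline mutations forming the familial breast cancer in Tatarstan and Bashkortostan republics". Section 13.2 repeats it as a measure to be analysed.
- Section 13.3, investigated group: clinical features of hereditary breast cancer and "revealed clinically significant (pathogenic) germline mutations in DNA-repair genes".
- Section 13.3, control group: "The control group will be consisting of patients with sporadic BC without germline mutations in DNA-repair genes".

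No section limits the mutation status or the frequency to particular types of mutation.

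**The concern.** Read in its ordinary sense, a search for nucleotide variation covers substitutions and short insertions or deletions. A deletion or duplication of a whole exon is a change in copy number, and no written step measures copy number. A familial patient whose only pathogenic change is of that kind will be recorded as having none.

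For the frequency objective this is a one-directional error. The planned 95% confidence interval describes sampling error only, so it would not reveal the bias. The 100% recall could reassure a reader that nothing is missed, but it describes one reference sample, and the text does not say that exon-level events were part of that test.

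The point matters in this study because Section 1.2 argues that the mutation spectrum in non-Slavic populations is poorly known and calls the programme comprehensive. The documents therefore give no ground for presuming that the missed share is negligible in Tatarstan and Bashkortostan.

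**Working it through.** **Inputs from the documents.** Section 14 gives a frequency of clinically significant mutations in familial breast cancer of 65%, 120 patients per group, about 390 tested for 240 enrolled, and PD-L1 high rates P0 = 0.14 and P1 = 0.30 with two-sided α = 0.05 and β = 0.2.

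**Assumed input.** L is the share of pathogenic mutations that are exon-level, with one such mutation per carrier. The documents give no value. I use 2–10%.

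**The plan's own figures.**
- Sample size: A = 1.960 × √(0.22 × 0.78 × 4) = 1.624 and B = 0.842 × √(2 × 0.21 + 2 × 0.1204) = 0.684. N = (1.624 + 0.684)² / 0.16² = 208, as stated. With continuity correction the total is 234, as stated.
- Testing: 240/390 = 61.5%, a screen-failure rate of 38.5%, inside the stated 35–40%.

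**Familial frequency.** The plan does not say how the 65% was measured, so both readings are shown.
- Reading A: 65% is what a nucleotide-only method finds. True frequency = 0.65/(1 − L); carriers missed per 120 found = 120L/(1 − L).
- Reading B: 65% is the true value. Observed frequency = 0.65(1 − L); familial patients to test for 120 found = 120/[0.65(1 − L)], against 120/0.65 = 185 with nothing missed.

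| L | A: true frequency | A: missed per 120 found | B: observed frequency | B: familial patients to test |
|---|---|---|---|---|
| 2% | 66.3% | 2.4 | 63.7% | 189 |
| 5% | 68.4% | 6.3 | 61.8% | 195 |
| 10% | 72.2% | 13.3 | 58.5% | 206 |

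**Against sampling error.** With 185 familial patients the 95% half-width at 65% is 1.96 × √(0.65 × 0.35/185) = 6.9 points. Under reading A the bias is 66.3 − 65 = 1.3 points at L = 2% and 72.2 − 65 = 7.2 points at L = 10%. The two are equal when 0.65/(1 − L) = 0.719, that is L = 9.6%.

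**Recruitment.** Under reading A the 65% yield already excludes the missed carriers, so there is no shortfall. Under reading B at L = 10%, 206 familial plus 120 sporadic patients make 326. If 10% of the sporadic patients tested were excluded as carriers (assumed), 120/0.9 = 134 would be needed, and the total is 340. Both are below 390.

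**Primary comparison.** With 120 per group, z = (0.16 × √240 − 1.624)/0.813 = 1.05, which gives power 85.4%. Here 0.813 is B without its factor 0.842. If the missed carriers are never replaced, so that the investigated group is 120(1 − L) against 120 controls, power is 85.0% at L = 2%, 84.5% at 5% and 83.6% at 10%.

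**Control group.** Let q be the share of sporadic patients who carry a panel mutation (assumed 5–10%). The undetected share among controls is qL/(1 − q(1 − L)). At L = 10% this is 0.005/0.955 = 0.5% for q = 5% and 0.010/0.910 = 1.1% for q = 10%. In the second case P0 becomes 0.14 + 0.011 × 0.16 = 0.142 and power is 84.5%.

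**The case against.** The strongest reply is that this is a scope limitation on a descriptive secondary objective, with an unknown size. Much of that stands. The 2–10% range has no anchor in the documents, and over most of it the bias is smaller than the sampling error. Section 3.1 ties its recall figure to one named sample and to exons plus flanking sequence; it never claims to cover copy-number changes. A figure in that subsection is not shown in the text reviewed, so a step drawn only there cannot be excluded.

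It does not remove the point. The written steps should stand on their own, a one-directional bias does not average out, and nothing in the plan tells a reader that the frequency omits a class.

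Two stronger readings are tempting, and the documents support neither.

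- A reader might infer that missed familial carriers are counted as mutation-free controls. Section 13.3 requires controls to be sporadic, so such a patient is a screen failure. The expected failure rate of 35–40% in Section 14 fits this, since 1 − 0.65 = 35%. The inference would matter if it were true: at L = 10%, missed carriers would be 0.065/0.415 = 15.7% of familial negatives, P0 would rise to 0.165 and power would fall to 69.9%.
- A reader might infer that the loss of carriers endangers recruitment. Under either reading of the 65%, the requirement stays inside 390.

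A further objection concerns the remedy. A depth-based call without a confirmatory assay could place a non-carrier in the investigated group. That is right, and the fix has to keep such calls out of primary group assignment.

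**Conclusion.** The point holds for the familial mutation frequency. As written, the pipeline calls nucleotide-level variants only, carrier status has no other source, and the error from the missed class runs in one direction. If 2–10% of pathogenic mutations are exon-level, an observed 65% corresponds to a true 66.3–72.2%; the bias reaches the size of the sampling error only near the top of that range. The figures rest on the assumed share, on one mutation per carrier, on about 185 familial patients tested (derived from 120/0.65, not stated in the plan), and on the missing figure containing no further step.

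The effects on the primary comparison, the control group and the number to be tested are small. This is a worthwhile and cheap improvement to a secondary objective, not a threat to the main result.

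**What to change.** First check the figure in Section 3.1 for a copy-number step. If there is none:

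1. **Pipeline (Section 3.1).** After alignment, add read-depth copy-number calling on the existing capture data, normalised across the samples in each run. Annotate and classify exon-level calls in panel genes in the same way as other variants.
2. **Frequency (Section 13.2).** Report the familial mutation frequency with and without exon-level calls, each with its 95% confidence interval.
3. **Groups (Section 13.3).** Keep primary group assignment on nucleotide-level calls. In one sensitivity analysis, exclude sporadic patients with an exon-level call from the control group, and add to the investigated group familial patients whose only finding is an exon-level call. The sensitivity analysis needs PD-L1 results for those familial patients, so their tumour samples should be stained although they do not enter the primary comparison.
4. **Performance statement (Section 3.1).** State that the 100% precision and recall are not shown to cover exon-level changes.

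The calling itself is one more software step on data with an expected coverage of 400x–600x, and it needs no new blood samples or sequencing. The other cost is PD-L1 staining for the few added familial patients, about 2 to 13 per 120 carriers found under the assumed range. Some depth-based calls will be uncertain. Reporting with and without them, and using them only in the sensitivity analysis, contains that.

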### Study Flow Chart

**Table 1** **Study Plan**

Study procedures	Screening/ Baseline Visit (day 0)	Biomarker analysis	
		Detection of presence/absence of germline mutations in DNA- repair system genes (NGS)  (1-3 months after day 0)	Estimation of PD-L1 expression level and TILs (IHC)  (1 month after NGS results)
Informed consent	X		
Patient demographics	X		
Medical history	X		
Inclusion / Exclusion criteria	X		
Receiving of blood samples for NGS	X		
Genetic testing		X	
Request of FFPE tumor tissue samples for IHC	X		
IHC			X
Disease information	X		

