**The planned timetable for the NIS is estimated to be as follows:**

First subject in	January 2018
Last subject in	January 2019
Study Database lock	March 2019
Final Study Report	July 2019

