## **12. DATA MANAGEMENT**

### **12.1 Collection, monitoring, processing of data and archiving**

Each enrolled patient would be assigned with unique identification number (the least available from the pre-designed sequence). The individual Case Report Form (CRF), specially designed for this study, will be completed for each patient enrolled.

The collection of data from out-patient medical records or disease histories for hospitalised patient, as well as collection of data received by a physician during the routine patient examination will be performed. Any special data collection procedures are not stipulated within the framework of this study. All patient data will be recorded by the participating physician both in the source documents and in the CRF. Source documents are kept by physician.

Signed Informed Consents will be kept by the physician during the study and after the study completion.

Database will have to be completed, and then passed appropriate quality check, considered to be full and accurate, and then will be locked. Collected data will be analyzed.

Essential study documents must be retained by the participating physician for as long as needed to comply with local and international regulations. No source documents, containing patients' personal data, should be taken away from the physician.

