### **12.2 Reporting and publication of data**

- Investigators will prepare a Non-Interventional Study Report within 6 months after completion of the last subject.
- The results from the NIS will be presented to the Investigators as a Study report at Q4, 2019.

In accordance with the Declaration of Helsinki, both authors and publishers have ethical obligations. In publication of the results of the NIS, the authors are obliged to preserve the accuracy of the results. Negative as well as positive results should be published or otherwise publicly available.

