## **14. DETERMINATION OF SAMPLE SIZE**

Today the data of PD-L1 expression level in breast cancer are limited. There are a few number of studies, which evaluated the frequency of PD-L1 expression in different breast cancer variants and the data of PD-L1 expression level in these studies are very differentiated depends on diagnostic approach, clone of antibodies and cut-off. We have calculated 2 variants of sample size based on minimal and maximal literature quantity data, using the Chi-squared statistic (or z test). Due to the absence of exact data about PD-L1 expression in hereditary and sporadic breast cancer we calculated the sample size based on data from general BC population (mainly is represented by sporadic BC) and TNBC (significant part of which is represented by hereditary BC). In the articles used as basis for calculation the authors assessed PD-L1 expression in tumor cells and the cut-off for PD-L1 positivity was 5%. In 2 studies estimated PD-L1 expression in total BC population as 4% and in TNBC as 11% the SP142 clone was used for IHC. We have found the only one study assessing concordance between SP142 and SP263 antibodies clones for IHC (on a subset of cases including BC) and the concordance was 95%. We are planning to assess the PD-L1 expression in both tumor and immune cells and use the 25% of PD-L1 positive cells as cut-off.

Considering the listed above we assume that the sample size will be near to a mean value between these two calculations.

Near 120 patients with breast cancer who have mutations in DNA-repair system genes and near 120 patients with breast cancer without mutations will be enrolled to the study in 2 centers:

Tatarstan Cancer Center, Kazan and Bashkortostan Clinical Oncology Center, Ufa. We will need to test near 390 patients for enrolling 240 patients (expected screen failure rate 35-40%). This data are based on the results of own pivotal study which has shown the frequency of clinically significant mutations in genes of DNA-repair system in familial BC 65%.

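### Is a March 2019 database lock too early for the last patients' mutation and PD-L1 results to be in?

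*Combined protocol and SAP*

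**What the plan says.** Table 1 (Study Plan) puts consent, eligibility and blood sampling at day 0. The NGS result, which decides whether a patient belongs to the mutation or the control group, is due "1-3 months after day 0". The PD-L1 and TIL assessment, which gives the primary variable, is due "1 month after NGS results".

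The synopsis and the timetable in section 11 both give first subject in January 2018, last subject in January 2019, lock in March 2019 and final report in July 2019. Section 11 introduces these dates with "The planned timetable for the NIS is estimated to be as follows".

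Section 12.1 sets the condition for lock: "Database will have to be completed, and then passed appropriate quality check, considered to be full and accurate, and then will be locked".

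The documents do not define when a subject counts as in. Section 13.3 ties the All Enrolled set to consent ("All Enrolled set will consist of all the subjects who signed informed consent to enter the study") but then says that patients are enrolled 1:1 into two groups that only the NGS result can define. Section 14 counts the 240 after testing: "We will need to test near 390 patients for enrolling 240 patients". Section 12.2 asks for the report "within 6 months after completion of the last subject".

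**The concern.** Adding Table 1's intervals to the January 2019 date gives a last PD-L1 result in March at the earliest and May at the latest, against a lock in March. At the long end, even group membership is unknown until April. The documents also give no rule for patients whose NGS or staining is still pending at lock.

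If the database were locked on schedule regardless, late entrants would drop out of the primary comparison for lack of an outcome, a group or both. The planned 240 leaves little to spare over the sizes in section 14: 234 with continuity correction and 208 without. A loss of a few dozen patients could take power below the intended 80%.

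**Working it through.** **Inputs.** Last subject in January 2019 and lock March 2019 (synopsis; section 11), with no day given. NGS 1 to 3 months after day 0 and staining 1 month later (Table 1). Rates 14% and 30%, two-sided 5% level, 80% power, 1:1 (section 14, third calculation).

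**The plan's own figures.** The stated lock month is reproduced at the short end of Table 1: January + 1 + 1 = March. The stated sample size also holds. (1.624 + 0.684)² / 0.16² = 5.327 / 0.0256 = 208. The continuity correction is 1 / (0.5 × 0.16) = 12.5, rounded to 13, giving 104 + 13 = 117 per group and 234 in total.

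**Reading 1: last subject in means day 0.** Date of last result = day 0 + NGS time + 1 month.

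| NGS time | Group known (day 0 from 1 to 31 January) | PD-L1 result | Within March? |
|---|---|---|---|
| 1 month | 1 to 28 February | 1 to 28 March | Yes, for a lock on 31 March, with 3 to 30 days left |
| 2 months | 1 to 31 March | 1 to 30 April | No |
| 3 months | 1 to 30 April | 1 to 30 May | No |

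The longest NGS time that still meets a 31 March lock is about 1.9 months for entry on 1 January, 1.5 months for 15 January and 0.9 months for 31 January.

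**Reading 2: last subject in means entry to a group after NGS.** Only the staining month remains: January + 1 = February 2019. The March lock fits.

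**What happens if NGS is slow on reading 1.** There are two possible paths.

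- *Follow section 12.1.* Results are outstanding, so the database is not complete and lock waits. With the last result in May, lock moves to May at the earliest, or June with query time. All patients keep their group and outcome. With 120 per group, the usual normal approximation gives z = (0.16 × √120 − 1.960 × √(2 × 0.22 × 0.78)) / √(0.30 × 0.70 + 0.14 × 0.86) = (1.753 − 1.148) / 0.575 = 1.05, so power is 0.85.
- *Lock in March regardless.* This breaches section 12.1. Assuming even accrual (not stated in the documents), NGS at the full 3 months for all late patients, and first, last and lock dates varied within their stated months, 21 to 60 of 240 would lack a PD-L1 result. The 60 needs a last entry on 31 January and a lock on 1 March. With losses split equally, power at 219, 200 and 180 patients is 0.82, 0.78 and 0.74. The margins are 240 − 208 = 32 patients without continuity correction and 240 − 234 = 6 with it.

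Only the second path costs power, and the plan rules it out.

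**The case for a change.** The best case for a change is that reading 1 is the more natural one. Consent and eligibility sit at day 0, the inclusion criteria in section 4.2 require no mutation result, and there is only one visit. On reading 2, a first subject in January 2018 would need a day 0 between October and December 2017, before the timetable begins. The July 2019 report is exactly six months after January 2019, which suggests that the single visit was taken as completion and laboratory time was overlooked. New dates and a definition would cost little and would spare the team a choice at lock between breaching section 12.1 and dropping late patients.

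Part of this stands. The term is undefined, and on reading 1 the March date is optimistic. But the text is mixed: section 13.3 enrols patients into groups that NGS defines, and section 14 speaks of testing about 390 to enrol 240, with a screen-failure rate. Nor is the choice at lock open, since section 12.1 settles it in favour of waiting.

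Stopping recruitment earlier is not cheap on the reading that creates the conflict. If day 0 is consent, about 390 patients pass through it. Closing at the end of October 2018 would then need about 390 / 10 = 39 a month instead of 390 / 12 = 32.5. The smaller rise, 240 / 10 = 24 against 240 / 12 = 20, counts only those who end up in a group.

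The margin of 6 patients also overstates the fragility. It comes from a continuity-corrected chi-squared sizing, whereas section 13.4 plans a logistic regression.

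**Conclusion.** The calendar arithmetic is right, but no change to the plan follows. If the last subject is counted at consent, the estimated March lock is reachable only with NGS at about 1 month for the last entrants, always under 2. If counted after NGS, it fits. In the unfavourable case the lock moves by roughly two months, to May 2019, or three with query time, and the July report may move with it. If completion is taken as the last staining result, the six-month report limit runs from May to November 2019, still within the fourth-quarter presentation that section 12.2 foresees.

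Neither the comparison, the data nor the power changes: 240 patients still give 0.85 for 14% against 30% without continuity correction. This rests on the study team observing section 12.1 and waiting for outstanding results, which is what the plan requires and what any data manager would do. Stating what last subject in means would be tidy, but it is an administrative detail with no effect on the conclusions.

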## 1. INTRODUCTION

### 1.1 Background

Breast cancer (BC) occupies the first place among malignancy in females (29.9% of all tumors in female patients in Russian Federation in 2015) [1].

One of the most perspective direction of the oncotherapy is anticancer immunotherapy – employment of inhibitors of immune checkpoints. Immune checkpoints inhibitors (such as anti-PD-1 and anti-PD-L1 antibodies) have shown good clinical efficiency in clinical research to cure such malignant tumor with high mutation load, as melanoma, lung cancer, and others.

One of the hypothesis of such effect states that, usually, more cancer neoantigens are synthetized in the tumors with high mutation load (driven by genome instability), causing severe lymphoid infiltration [2-3]. This situation is balanced by overexpression of such inhibitors of the immune response as PD-1 and PD-L1 [4 - 6].

Breast cancer – is relatively heterogenic tumor, with different genetic, morphological and phenotypic forms.

Despite relatively low expression of PD-L1 in BC in general, there are reasons to believe that genetic instability, driven by mutations in genes involved in DNA repair, can increase the immunogenicity and, thus, the expression of PD-L1 in BC.

To date, it is widely accepted that 5-10% of BC cases are represented by hereditary types, i.e. mediated by germline pathogenic mutations in genes of DNA reparation pathways. Hereditary breast cancer (HBC), as well as ovarian cancer (OC), caused by mutations in genes BRCA1, BRCA2, CHEK2, TP53 и PTEN, and others. Thus, one of the promising directions here is to understand the inter-relation among germline pathogenic mutations associated with HBC, and activity of PD-L1. It would allow to optimize selection of anti-PD-L1 therapy, by forming group of patients (matching criteria of HBC) with high level of PD-L1 expression in cancer cells and tumor-infiltrating lymphocytes.

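### PD-L1 staining follows each patient's own NGS result and nothing balances IHC runs between carriers and controls, so assay drift could be confounded with group

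*Combined protocol and SAP*

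**What the plan says.** Table 1 (Study Plan) places germline testing at "1-3 months after day 0" and the PD-L1 and TIL assessment at "1 month after NGS results". IHC therefore falls about 2 to 4 months after each patient's visit. The rule is the same for both groups. FFPE tissue is requested at the baseline visit.

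Section 13.3 states the allocation as "All patients will be enrolled in 2 groups 1:1". Section 14 gives it as totals, about 120 carriers and "near 120 patients with breast cancer without mutations will be enrolled to the study in 2 centers". Carrier status is known only once the NGS result is back. First and last subject in are planned for January 2018 and January 2019, with database lock in March 2019.

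Section 8.1 defines the primary variable by the percentage of stained tumour or immune cells, cut at 25%. Section 3.1 names one antibody clone (SP263) and one laboratory in Kazan. Section 13.4 specifies logistic regression with an odds ratio and 95% confidence interval and names no term for IHC run, lot, reader or date. Section 13.1 defers a full SAP to a later date, before database lock. I found no rule on the make-up of staining runs, antibody lots or concurrent accrual of the two groups.

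**The concern.** A percentage of stained cells judged against a 25% cut-off can move with the staining run, the antibody lot or the reader's threshold. If the groups are stained over the same period, such a change affects both alike and largely cancels in the comparison. If one group is stained mostly earlier, the change enters the group difference directly and can create an apparent mutation effect or hide a real one.

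The plan does not prevent this. Staining follows the individual clock and the 1:1 ratio need hold only at the end, so the timing of the groups depends on how fast each happens to accrue. Using one clone and one laboratory removes differences between clones and sites, but not change over time. Masking the reader to mutation status or adjusting for centre would not remove it either. If run and group cease to overlap, adding run or date to the model cannot separate them.

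**Working it through.** **The plan's own figure.** Section 14, third calculation: P0 = 0.14, P1 = 0.30, two-sided alpha 0.05, power 80%, 1:1.

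- A = 1.960 × √(0.22 × 0.78 × 4) = 1.624
- B = 0.842 × √(2 × 0.30 × 0.70 + 2 × 0.14 × 0.86) = 0.684
- N = (1.624 + 0.684)² / 0.16² ≈ 208, or 104 per group, as stated. With the continuity correction it is 117 per group, also as stated.
- At the planned 120 per group, power is 0.854 by the normal approximation.

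**Which group would be stained earlier?** Suppose patients enter at a constant rate and a share c of eligible patients are carriers. The time to fill the control quota, divided by the time to fill the carrier quota, is c/(1 − c).

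| c | c/(1 − c) | Quota filled first |
|---|---|---|
| 25% | 0.33 | controls |
| 40% | 0.67 | controls |
| 50% | 1.00 | neither |
| 60% | 1.50 | carriers |

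The documents do not give c for the recruited mix. Balance arises only near 50%, and nothing in the plan secures it.

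**Size of the bias.** Let s be the change in the PD-L1-high rate between early and late staining, and g the difference between the groups in the share stained late. The bias in the risk difference is s × g, and is zero if either is zero. Both are assumptions.

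**Type I error.** The true rate is 14% in both groups with 120 per group. The group stained early stays at 14% and the other is observed at 14% + s × g. The test is a two-sided pooled z test, with rejection probabilities summed over the two binomial distributions.

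| Drift s | g = 0.5: observed rates | Type I error | g = 1: observed rates | Type I error |
|---|---|---|---|---|
| 4 points | 14% v 16% | 7.3% | 14% v 18% | 13.7% |
| 6 points | 14% v 17% | 9.9% | 14% v 20% | 23.9% |
| 8 points | 14% v 18% | 13.7% | 14% v 22% | 37.0% |

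Hand check for 14% v 20% by the normal approximation: pooled SE = √(2 × 0.17 × 0.83 / 120) = 0.0485; unpooled SE = √((0.14 × 0.86 + 0.20 × 0.80) / 120) = 0.0483. The upper-tail argument is (0.06 − 1.96 × 0.0485) / 0.0483 = −0.725, so the rejection probability is about 23.5%, close to the exact 23.9%.

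With balanced runs (g = 0) the type I error is about 5% whatever the drift.

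**Power, if later staining reads lower and carriers are the later group.** For 14% v 30% and a fall of 5 points (normal approximation):

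- g = 0.5, with 25% of controls and 75% of carriers stained late: observed 12.75% v 26.25%, power 0.755.
- g = 1: observed 14% v 25%, power 0.576.

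Both compare with 0.854 when there is no drift.

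**The case against.** The strongest reply is that Table 1 applies one rule to both groups and so creates no difference between them. It also gives approximate intervals, and does not forbid grouped runs. That is right. The defect is the absence of any rule on concurrency or run balance; the timing rule merely leaves staining to follow accrual.

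A reader might go further and infer that controls will fill first and that early runs will be mostly controls, because section 1.1 says "5-10% of BC cases are represented by hereditary types". The documents do not support this. Section 14 plans to test about 390 patients. At 5 to 10%, 390 unselected patients would yield only about 20 to 39 carriers (390 × 0.05 and 390 × 0.10), far short of 120. The budget rests instead on a 65% mutation frequency in familial breast cancer, at which 120 carriers need about 185 familial patients (120 / 0.65). With recruitment enriched in this way, the order is unknown and could reverse.

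It is also fair to say that the documents give no drift, and that 4 to 8 points on a base of 14% is a relative change of 29 to 57%. The timing gap is equally assumed, and complete separation is the extreme case. The error rates illustrate the risk and do not predict it.

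Confounding would not be beyond all rescue: if tissue remained, re-staining a mixed subset could measure drift directly. The later SAP could add a run or date term. Neither is as good as prevention. Tissue may run out, and a SAP written shortly before lock cannot restore overlap once slides are stained.

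**Conclusion.** The point holds as an unprevented risk to the primary comparison. Nothing in the plan keeps IHC run, lot or reading period balanced between carriers and controls. It does not show that the groups will separate in time, that controls come first, or that the assay will drift.

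With both quantities assumed, the type I error is about 7 to 14% for a drift of 4 to 8 points at half separation and 14 to 37% at full separation, against about 5% with balanced runs. The direction of any bias is unknown. The planned sample size is not affected. The change is worth making before staining begins, because prevention is cheap and later correction depends on spare tissue or on overlap that may not exist.

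**What to change.** 1. Replace the per-patient IHC timing in Table 1 with staining and reading of stored FFPE slides in batches that hold carriers and controls in about equal numbers.
2. Record IHC run, antibody lot and staining date for every slide.
3. Recruit familial and sporadic patients concurrently through the year. Do not tie each control to a carrier who is already confirmed. Such a control would enter 1 to 3 months after the carrier's visit and, on the current clock, be stained 2 to 4 months after that. For a carrier entering in January 2019 this means about April to August 2019, after the March 2019 lock.
4. State in the SAP a sensitivity analysis of the primary logistic model with IHC run or calendar period as a stratum.

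The cost is scheduling, three laboratory data fields and one extra analysis, with no additional patients, slides or readers. The downside is delay: some slides from the faster-accruing group would wait for a mixed run, possibly for some months. Batch dates must be fitted to database lock, where the margin is already thin: under the present rule, a patient entering in January 2019 has IHC in March to May 2019, against a lock in March 2019.
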